12.0 ETHICS**12.1 INSTITUTIONAL REVIEW BOARD (IRB)/RESEARCH ETHICS BOARD (REB)**

The study protocol, protocol amendments, informed consent forms, and other relevant documents (e.g., recruitment advertisements) will be reviewed and approved by the IRB/REB prior to site initiation. All correspondence with the IRB/REB should be retained in the site's trial file with copies of IRB/REB communications forwarded to the Sponsor.

A protocol amendment may be implemented prior to IRB/REB approval only where the change is necessary to eliminate apparent immediate hazards to the participants. Should this occur, the investigator must notify the IRB/REB and the Sponsor in writing immediately after the implementation of the protocol amendment. No deviations to the protocol are permissible except when necessary to eliminate an immediate hazard to study participants. The investigator shall notify the IRB/REB of deviations from the protocol or serious adverse events occurring at the site, in accordance with local procedures.

12.2 ETHICAL CONDUCT OF THE STUDY

The study will be conducted in accordance with the *Declaration of Helsinki on Ethical Principles for Medical Research Involving Human Participants*, adopted by the General Assembly of the World Medical Association (2013).

In addition, the study will be conducted in accordance with the protocol, the International Conference on Harmonisation guideline on *Good Clinical Practice*, and applicable local regulatory requirements and laws.

12.3 SUBJECT INFORMATION AND CONSENT

Informed consent will be administered in accordance with the requirements of 21 CFR 50.20-27, FDR C.05.010 and ICH E6 4.8, Principles of Good Clinical Practice, as applicable. Before protocol-specified procedures are carried out, the PI and study staff will explain the objectives of the study, study procedures, as well as

the risks involved to the study participant, his/her legally authorized representative (if applicable) and caregiver/informant prior to their inclusion in the trial.

Prior to performing any study-specific procedure, each study participant and the participant's caregiver/informant will be required to read and voluntarily sign an Institutional Review Board (IRB)/Research Ethics Board (REB) - approved informed consent form (ICF), indicating his/her consent to participate (or assent [where this is in accordance with local laws, regulations and ethics committee policy] in the case of participants who are deemed to be unable to have the cognitive ability to provide consent). This ICF will conform to the requirements of the applicable 21 CFR 50.20-27, FDR C.05.010 and ICH E6 Principles of Good Clinical Practice (GCP). The Study Sponsor must agree with the final IRB/REB-approved ICF prior to initiation of the study. Study participants will be provided adequate time to review the ICF and if they wish, may take it home to discuss their participation in the study with friends, family, and/or a physician. The original signed ICFs must remain in the study participant's file in the Study Site. Study participant will receive a copy of their signed ICF.

Continued consent / assent will be evaluated at each study visit for the duration of the study.

13.0 STUDY TERMINATION CRITERIA

The study may be terminated prematurely as a result of a regulatory authority decision, IRB/REB decision, or at the discretion of the Sponsor. In addition, the Sponsor retains the right to discontinue development of azeliragon at any time.

Should the study be prematurely terminated, the Sponsor will promptly notify the investigator. Following notification, the investigator must contact all participating participants and the hospital pharmacy (if applicable) within 30 days.

25. Thomas RG. et al. Longitudinal decline in mild-to-moderate Alzheimer's disease: Analyses of placebo data from clinical trials Alzheimer's & Dementia: The Journal of the Alzheimer's Association. 2016. Volume 12, Issue 5, 598 – 603.

APPENDICES

APPENDIX 1

CRITERIA FOR SAFETY VALUES OF POTENTIAL CLINICAL CONCERN

Criteria for Safety Values of Potential Clinical Concern

Hematology

Assay	Lower limit of the normal reference range (LLN)	Upper limit of the normal reference range (ULN)
Hemoglobin	<0.8 times	>1.2 times
Hematocrit	<0.8 times	>1.2 times
RBC	<0.8 times	
Platelets	<0.5 times	>1.75 times
WBC	<0.6 times	>1.5 times
Total Neutrophils (abs)	<0.8 times	>1.2 times
Eosinophils (abs)		>1.2 times
Monocytes (abs)		>1.2 times
Basophils (abs)		>1.2 times
Lymphocytes (abs)	<0.8 times	>1.2 times

Chemistry

Assay	Lower limit of the normal reference range (LLN)	Upper limit of the normal reference range (ULN)
Total bilirubin		>1.5 times
AST		>3 times
ALT		>3 times
GGT		>3.0 times
Alkaline Phosphatase		>3.0 times
Creatinine		>1.5 times
BUN		>1.3 times
Glucose	<0.6 times	>1.5 times
Uric acid		>1.5 times
Sodium	<0.95 times	>1.05 times
Potassium	<0.9 times	>1.1 times
Calcium	<0.9 times	>1.1 times
Albumin	<0.8 times	>1.2 times
Total protein	<0.8 times	>1.2 times
Bicarbonate	<0.9 times	>1.1 times
Chloride	<0.9 times	>1.1 times

APPENDIX 2

PROHIBITED MEDICATION LIST

Prohibited Medication List

The following medications are NOT ALLOWED as concomitant medications during the study. The list is not exhaustive and therefore, the Investigator is asked to contact the Medical Monitor and/or the Sponsor for clarification regarding the acceptability of similar agents not mentioned here.

Drugs known to be strong CYP 2C8 inhibitors: NOT ALLOWED

gemfibrozil

clopidogrel

Flockhart DA. Drug Interactions: Cytochrome P450 Drug Interaction Table. Indiana University School of Medicine (2007). "<http://medicine.iupui.edu/clinpharm/ddis/clinical-table/>" Accessed 17 Nov 2017.

Clinical Drug Interaction Studies — Study Design, Data Analysis, and Clinical Implications Guidance for Industry *DRAFT GUIDANCE*. October 2017.

TTP Translational Technology®, TransTech's (now vTv Therapeutics) proprietary drug discovery engine, was employed to develop TTP488, which is an orally bioavailable antagonist of the Receptor for Advanced Glycation Endproducts (RAGE). This product is being developed as a potential treatment for AD.

These studies are designed to evaluate the safety and efficacy of azeliragon as a treatment for subjects with mild Alzheimer's disease and impaired glucose tolerance.

This study is planned with an enrichment strategy, following the draft regulatory guidance depicted in the FDA guidance *Enrichment Strategies for Clinical Trials to Support Determination of Effectiveness of Human Drugs and Biological Products* (March 2019). The statistical analysis is planned to conform to FDA guidance provided in Draft Guidance *Early Alzheimer's Disease: Developing Drugs for Treatment* (February 2018), review templates provided by the FDA, and *Guidance for Industry: Providing Clinical Evidence of Effectiveness for Human Drug and Biological Products* (CDER&CBER, 1998).

The goals of this statistical analysis plan (SAP) are the following:

- To describe the approach of statistical analysis in order to support scientifically sound study conclusions for Part 1 of TTP488-305.
- To conform to regulatory guidance to facilitate the use of the statistical evaluation for support in the regulatory review of study results for purposes of product registration.
- To guide the analysis and reporting of study results to enable the production of valid and accurate depictions of study data.

The approach will conform to FDA guidance as described in *Guidance for Industry Statistical Principles for Clinical Trials* (1998).

1.1 Study Objectives

The primary objective of this study is:

- To evaluate the impact of 6 months of treatment with oral azeliragon on cognitive performance

The secondary objectives of this study are:

- To evaluate the efficacy of azeliragon treatment on measures of function and activities of daily living
- To evaluate the efficacy of azeliragon treatment on complications of diabetes
- To evaluate the safety and tolerability of 6 months of azeliragon treatment
- To evaluate the effect of azeliragon treatment on biomarkers and markers of inflammation

1.2 Study Rationale

Analysis of study TTP488-301 demonstrated potential beneficial effects of azeliragon that increased with higher baseline HbA1c value. This finding is consistent with the hypothesis that the TTP488-301 RAGE antagonist may have beneficial effects in patients who have overexpression of RAGE. HbA1c is being used as a marker for increased RAGE expression because research has shown a correlation of increased HbA1c with increased RAGE in a group of diabetic elderly patients with MCI (as well as a correlation of increased RAGE with increased AGEs). Further, patients with diabetes and HbA1c have increased AGE accumulation where AGEs bind to RAGE and promote increased expression of RAGE. (Gorska-Ciebiada 2015)

This study is an adaptive learn-and-confirm study to confirm TTP488-301 diabetes subgroup findings at 6 months (in Part 1) as well as use the information in Part 1 to refine the protocol for Part 2.

1.3 Subject Population

The study population includes subjects with a clinical diagnosis of probable mild AD (screening MMSE between 21 and 26, inclusive; baseline MMSE between 19 and 27, inclusive; CDR-global of 0.5 or 1 at screening and baseline; ADAS-cog14 score of at least 10 at screening and baseline) and screening HbA1c of 6.5% - 9.5%. The study population includes subjects who have a reliable caregiver with regular contact (i.e., 10 hours a week as combination of face-to-face visits and telephone contact acceptable) who will facilitate the subject's full participation in the study. Caregivers must have sufficient subject interaction to be able to provide meaningful input into the rating scales administered in this study where caregiver input is required, in particular the CDR, A-IADL, and FAQ and evidence of this should be documented in source

documentation. Participants who reside in assisted living facilities are permitted provided that they meet caregiver criteria. Subjects are between 50 and 85 years of age, inclusive.

1.4 Randomization

A total of 100 subjects were originally planned to be randomized into Part 1 of this study, but the total enrolled was 43 due to a slow enrollment and sponsor decision to stop enrollment due to the additive impact of the COVID pandemic on enrollment rates. Subjects were enrolled and randomized according to a fixed randomization scheme blocked by study investigative site.

Randomization is intended to have balanced allocation (1:1) between active and placebo. Dropouts will not be replaced.

1.5 Study Design

TTP488-305 is a protocol that consists of two sequential, multi-center, randomized, double-blind, placebo-controlled, parallel group studies operationally conducted under a single protocol. The purpose of the study is to evaluate the safety and efficacy of 5 mg/day oral azeliragon relative to placebo in subjects with mild Alzheimer's disease (screening MMSE 21-26, baseline MMSE 19-27 and ADAS-cog14 score of ≥ 10) and impaired glucose tolerance (Screening HbA1c 6.5% - 9.5%, inclusive). Eligible participants will be randomly assigned to azeliragon or placebo in a 1:1 randomization for a double-blind dosing period of 6 months (Part 1) or 18 months (Part 2). The Part 1 and Part 2 studies will have independently randomized, unique study populations.

The Part 1, 6-month, double-blind treatment portion of the study will include 5 clinic visits. The primary objective of the Part 1 portion is to evaluate the efficacy of 6 months of oral azeliragon on a measure of cognition (ADAS-cog14). Secondary objectives of Part 1 will be to evaluate the efficacy of 6 months of oral azeliragon on multiple measures of function (CDR, Amsterdam-IADL, FAQ) to inform selection of a functional endpoint to serve as co-primary in Part 2. Additionally, Part 1 will be used to inform the sample size required to adequately power Part 2 of this study. The Schedule of Activities for Part 1 is described in Section 14 of this SAP.

Part 1 is conducted at multiple sites in the U.S and Canada.

The overall structure of the study includes the following periods:

Screening period: Screening procedures occur within 60 days of start of study drug administration, and they include obtaining informed consent and evaluations to determine eligibility for study participation.

Baseline Study Period: (Day -7 — Day 1, pre-dose): Subjects will have baseline assessments for efficacy and safety measures, including imaging and PK assessments.

Treatment Period: (Day 1 — Month 6): Subjects are treated with double-blind study medication. Efficacy and safety measures are taken. Blood samples are taken and subjects have assessments for safety and PK.

Follow-up period: (Month 9): Subjects return to the site for final safety assessments including vital signs, adverse events, electrocardiography and concomitant medications are taken. Blood draws are taken for safety evaluations and for pharmacokinetics evaluations.

1.6 Sample Size and Power Considerations

Original Sample size considerations for Part 1 (from protocol):

Assuming a standard deviation of the change from Baseline to Month 6 in ADAS-cog14 of 4, using $\alpha = 0.05$, a total sample size of approximately 82 subjects in balanced allocation (41 subjects per group) provides at least 90% power to detect a difference between treatment groups of 2.9 using a 2-sided, 2-sample t-test. Assuming a dropout rate of 18% or less, randomization of 100 subjects provides adequate statistical power for Part 1 to demonstrate superiority of azeliragon over placebo based on the ADAS-cog14. (Section 9.2).

Recalculated power considerations for Part 1:

ADAS-Cog: Estimates and standard deviations were drawn from a model that fit change in ADAS-Cog11 over time using the data from the STEADFAST A-study and B-study combined (N=880). The model utilized all individuals in the study. Estimates were drawn at an HbA1C of 7.2 (average from present TTP488-305 study; Part 1). The estimates of standard deviation and effect size for the change from baseline in ADAS-Cog was 3.4 and -1.54 respectively. Given a sample size of 43, a two-sided α of 0.05 would result in 30% power to detect a significant effect. If we observe the estimated effect size and standard deviation at the given sample size in Part 1 of the current study (TTP-305) we would expect to observe a p-value of 0.144 which could be considered evidence of a trend.

Previous studies (Siemers et al 2016) suggest that mean to standard deviation ratio between ADAS-Cog 11 and 14 are similar, therefore it is expected that the estimates drawn using ADAS-Cog11 will be applicable to ADAS-Cog14 data.

Cognitive Composite: The association of treatment was also tested using a composite that was derived from STEADFAST A and B studies. Composites allow the global assessment of multiple aspects of disease as well as exclusion of items that do not contribute to progression and thus add noise to the data. The composite is composed of the ADAS-Cog comprehension, word finding difficulty, and remembering test instructions variables. The composite will be calculated by summing the within visit z-scores for each item across individuals. Z-scores are calculated by subtracting the individual item score at visit x from the baseline mean item score and dividing this value by the item standard deviation at baseline.

The ADAS-Cog variables included in the model were chosen using PLS regression where treatment status at 6 months was the outcome variable and ADAS-Cog 11 and CDR-SB individual items were predictor variables. The PLS was modeled using

STEADFAST study B as this dataset showed a smaller ADAS-Cog effect with treatment.

PLS estimates and standard deviations were drawn from the STEADFAST data (A-study and B-study combined) as above for ADAS-cog. The model fit change in PLS over time with estimates drawn at an HbA1C of 7.2. The estimates of standard deviation and effect size for the change from baseline were -0.92 and 1.5, respectively. Given a sample size of 43, an alpha of 0.05 would result in 49% power to detect a significant effect. If we observe the estimated effect size and sd at the given sample size in the present study (Part 1) we would expect to observe a p-value of 0.052 indicating that the composite is somewhat more sensitive to treatment effects than the ADAS-cog 11.

Modified Cognitive Composite: The STEADFAST analysis indicates that a portion of the observed change may be due to age-related cognitive decline. To assess this, a modified composite that incorporated aspects associated with cognitive decline due to aging, specifically trail making test (TMT A/B) and Controlled Oral Word Association Test (COWAT) was generated. As these variables are not available in ELEVAAGE, historic data (ADNI) was used to identify the best surrogate for each. All surrogates were found to be within ADAS-Cog individual items. Word finding difficulty was found to be a suitable surrogate for TMTA, while delayed word recall and ideational praxis were surrogates for TMTB ($r=0.5$, 0.6 , and 0.6 respectively). The COWAT surrogates were orientation and word recognition ($r=0.5$ at 12 months). (delayed recall, ideational praxis, orientation, and word recognition).

The model fit change in PLS over time with estimates drawn at an HbA1C of 7.2. The estimates of standard deviation and effect size for the change from baseline were -1.73 and 2.9, respectively. Given a sample size of 43, a two-sided alpha of 0.05 would result in 47% power to detect a significant effect. If we observe the estimated effect size and sd at the given sample size in the present study (Part 1) we would expect to observe a p-value of 0.059 indicating that the composite is somewhat more sensitive to treatment effects than the ADAS-cog 11.

1.7 Early Stopping, Data Monitoring, and Interim Analysis

There will be no interim analyses.

An adjustment for alpha is included in the original protocol, as a conservative measure to accommodate unblinded evaluations by the independent data monitoring committee (IDMC). The alpha adjustment is applied to accommodate up to 10 analyses by the IDMC because the safety evaluation will include review of ADAS-Cog data from the safety perspective. Alpha = 0.0001 is apportioned to each of no more than 10 analyses by the IDMC that includes review of ADAS-Cog data.

There will be two database locks: one for the double-blind treatment period, and one for the follow-up period. Final analysis will be performed on the interim database after all subjects complete the treatment period (Month 6 or Early Termination) and all Treatment Period data is locked. The final database lock will occur after all Follow-up Visits are complete.

1.8 Conformance to Regulatory Standards

An objective of this SAP is to comply with regulatory standards. The following guidance documents were specifically consulted in the preparation of this SAP:

- ICH E9: Statistical principles for clinical trials (September 1998); ICH and FDA
- ICH E9(R1): Estimands and sensitivity analysis in clinical trials (draft; October 2017); ICH and FDA.
- ICH E14: Clinical evaluation of QT/QTc interval prolongation and proarrhythmic potential for non-antiarrhythmic drugs (October 2012); ICH and FDA
- E14 Q&A (R3) ICH guideline E14: the clinical evaluation of QT/QTc interval prolongation and proarrhythmic potential for non-antiarrhythmic drugs (R3)—questions and answers (26 January 2016); EMA
- Guideline on adjustment for baseline covariates in clinical trials (26 February 2015); EMA.
- Guideline on the clinical investigation of medicines for the treatment of Alzheimer’s disease (Feb 2018); EMA.
- Good Review Practice: Statistical review template (30 July 2012). Office of Biostatistics; CDER; MAPP 6010.4
- Good Review Practice: Clinical review template (10 December 2010). Office of New Drugs; CDER; MAPP 6010.3
- Guidance: Providing clinical evidence of effectiveness for human drug and biological products (May 1998); CDER; CBER.
- Draft Guidance: Demonstrating Substantial Evidence of Effectiveness for Human Drug and Biological Products (Draft, December 2019); CDER, CBER.
- Good Review Practice: Reviewer guidance: Conducting a clinical safety review of a new product application and preparing a report on the review (February 2005); CDER.
- Draft guidance: Early Alzheimer’s Disease: Developing drugs for treatment (February 2018); CDER, CBER.
- Draft guidance: Adaptive designs for clinical trials of drugs and biologics (November 2019); CDER, CBER.
- Reflection paper on methodological issues in confirmatory clinical trials planned with an adaptive design (18 October 2007); EMA
- Draft guidance: Enrichment strategies for clinical trials to support Determination of effectiveness of human drugs and biological products (March 2019); CDER, CBER.
- Guidance: Drug-induced liver injury: premarketing clinical evaluation (July 2009); CDER, CBER.
- Guidance: Patient-reported outcome measures: Use in medical product development to support labeling claims (December 2009); CDER, CBER, CDRH.
- ICH and MISO. (March 2019). MedDRA Introductory Guide Version 22.0.
- FDA Guidance on Conduct of Clinical Trials of Medical Products during COVID-19 Public Health Emergency: Guidance for Industry, Investigators, and Institutional Review Boards. March 2020 . Updated on September 2020.

- FDA Guidance: Statistical Considerations for Clinical Trials During the COVID-19 Public Health Emergency Guidance for Industry. June 2020; CDER, CBER, CDRH, CVM.

The planned statistical analysis of this study is intended to comply with regulatory expectations and standards as depicted in the above-listed guidance documents.

1.9 Modifications from the Statistical Section of the Protocol

The power calculation was updated from the protocol and the composite score analysis was added. Secondary variables (MMSE and biomarkers) and exploratory assessment of ADAScog11 progression were added. In addition, the statistical analysis plan adds more detail and analyses and supersedes the statistical section of the protocol.

1.10 Adaptive Study

This study is an adaptive trial, which includes 2 studies under the same protocol. This SAP is focused on Part 1 of this adaptive study.

This SAP conforms to standards set forth in *Adaptive Designs for Clinical Trials of Drugs and Biologics Guidance for Industry* (CDER, CBER, November 2019). The intention of the adaptive nature of this protocol is to leverage potential advantages related to statistical analysis as depicted in the FDA final guidance.

2 Statistical Hypotheses

Part 1 has a single primary endpoint (ADAS-Cog14).

The testing sequence will be as follows for strict significance, however proof of concept will be attained by significance in any of the outcomes below (Figure 1):

The first set of hypotheses to be tested is as follows:

H₀₁: The mean change in ADAS-cog14 in the active group is equal to that of the placebo group*.

H₁₁: The mean change in ADAS-cog14 in the active group is not equal (is superior) to that of the placebo group*.

Conditional on statistical significance, testing will proceed hierarchically:

H₀₂: The mean change in A-IADL in the active group is equal to that of the placebo group.

H₁₂: The mean change in A-IADL in the active group is not equal (is superior) to that of the placebo group[§].

Conditional on statistical significance, testing will proceed:

H₀₃: The mean change in CDR-sb in the active group is equal to that of the placebo group.

H₁₃: The mean change in CDR-sb in the active group is not equal (is superior) to that of the placebo group[§].

Conditional on statistical significance, testing will proceed:

H₀₄: The mean change in FAQ in the active group is equal to that of the placebo group.

H₁₄: The mean change in FAQ in the active group is not equal (is superior) to that of the placebo group[§].

H₀₅: The mean change in the cognitive composites or GST in the active group is equal to that of the placebo group.

H₁₅: The mean change in the cognitive composites or GST in the active group is not equal (is superior) to that of the placebo group.

* ADAS-Cog will also be run using LZCF. If neither of these are significant, the cognitive composites and global statistical test (GST) will be assessed for significance to demonstrate proof of concept. It is acknowledged that the present study is underpowered to replicate the clinically meaningful effect size observed in the STEADFAST combined A- and B-study diabetes subgroup. Therefore, if the observed effect size (treatment difference) or percent slowing (treatment difference divided by the placebo change) is equal to or greater than the corresponding values from the STEADFAST pooled analysis (-0.92; -61%), this will be considered proof of concept. Lack of strict statistical significance is expected with this range of effect size due to the small n, but this result, in the context of the consistency of the effect seen in STEADFAST Part A with the STEADFAST Part B data would provide proof of concept for this compound.

§ All secondary variables will also be run using LZCF.

3 Estimand Specification

This SAP is constructed to conform to regulatory guidance. In particular, this section is included as recommended by ICH E9 (R1) Addendum on estimands and sensitivity analysis in clinical trials to the guideline on statistical principles for clinical trials (30 August 2017).

In accordance with ICH E9 Addendum, the specification of the estimand is included in this SAP with the 4 attributes detailed in ICH E9 Addendum, Section A.3.1:

- A. The Population, that is, the subjects targeted by the scientific question:
For this study, the population consists of subjects with AD and HbA1c of 6.5% - 9.5% who meet eligibility requirements for the study, receive double-blind medication, and have at least one valid post-baseline measure of ADAS-cog(14).
- B. The variable (or endpoint) to be obtained for each patient, that is required to address the scientific question:
For this study, the primary endpoint is Change in ADAS-cog(14).
- C. The specification of how to account for intercurrent events to reflect the scientific question of interest:
Due to the small sample size intercurrent events will not be accounted for in this analysis.
- D. The population-level summary for the variable that provides, as required, a basis for a comparison between treatment conditions:
For this study, the population-level summary for the variable is the least-squares mean (LSM) of the treatment difference in mean change from baseline in ADAS-cog(14).

4 Populations of Analysis

In accordance with guidance from the International Conference of Harmonization of Technical Requirements for Registration of Pharmaceuticals for Human Use (ICH) guideline ICH E9 Statistical Principles for Clinical Trials (1998), the following population will be used for all statistical analysis:

- The full analysis set (FAS) includes all randomized subjects, whether or not they receive any study medication, and who have at least one post-Baseline assessment.
- The per protocol set (PPS) includes all subjects in the FAS, except for those who are excluded because of major protocol violations, where a major protocol violation is one that may affect the interpretation of study results (e.g., taking less than 50% of prescribed study medication during participation).

Final determinations of the PPS will be made at the masked data review meeting held in accordance with ICH E9 prior to the lock data. The complete specification (made blinded to treatment arm) will be documented in the minutes to the blind data review meeting held prior to lock the data.

- The safety set (SAF) includes all subjects who receive any study medication.

The FAS will be used for all hypothesis tests of efficacy. Analysis of superiority using the PPS will also be done for supportive analyses. If the PPS does not differ from the FAS by at least 15%, the PPS is considered optional.

The SAF will be used for safety analyses.

5 Variables of Analysis

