Further examination of the data showed clear differences in rate of placebo decline in ADAS-cog between the STEADFAST study (3 points in 18 months), the azeliragon Phase 2b study (10 points in 18 months) and that published for other similar studies (6 points in 18 months [Thomas 2016]), which may explain the lack of detectable effect in the STEADFAST study (the study was powered to detect a 4 point difference in change from baseline between active and placebo at 18 months, assuming a placebo decline of approximately 6 points over 18 months). It is hypothesized that subjects with higher expression of RAGE would present more inflammation and neurodegeneration and decline at a faster rate.

It has been demonstrated that advanced glycation endproducts accumulate in tissues of patients with diabetes with expression of RAGE increasing in response to injury and increases in ligand concentrations, including AGEs. This interaction of AGEs, and other ligands of RAGE, leads to sustained cellular damage and inflammation thus contributing to complications of diabetes including retinopathy, neuropathy and nephropathy. Further it has been shown that accumulation of AGEs parallels the development of cognitive impairment and dementia in patients with diabetes. Thus, patients with diabetes represent a sub-group expected to have increased concentration of RAGE ligands, increased expression of the RAGE receptor, have the potential to decline at a more rapid rate and thereby likely to respond to an antagonist of RAGE.

A comparison of placebo-treated subjects in the diabetic subgroup (defined as HbA1c \geq 6.5%) and the non-diabetic (HbA1c < 6.5%) complement of the target analysis set (subjects with evidence of cognitive impairment at Baseline [ADAScog \geq 10]) is provided in [Figure 1](#). Interestingly, the data show a clear difference in the rate of cognitive decline between the placebo subjects with diabetes and the placebo subjects without diabetes. The diabetic, placebo-treated subjects had numerically greater decline from baseline in the ADAS-cog when compared with the non-diabetic, placebo treated subjects. These data further support the hypothesis that subjects with presumed higher expression of RAGE present more inflammation and neurodegeneration and decline at a faster rate.

Figure 1. Change from Baseline in ADAS-cog: Comparison of Placebo-treated patients with HbA1c at Baseline $\geq 6.5\%$ and HbA1c $< 6.5\%$ (TTP488-301 A-Study [Target Analysis Set])

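### The percent-slowing route to proof of concept has no direction condition, so a worse active arm can pass it, and the denominator behind its -61% benchmark is not reported

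*SAP*

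**What the plan says.** SAP Section 2 (Statistical Hypotheses), footnote *, is attached to the ADAS-cog14 hypothesis. It accepts that the study is underpowered and offers two further criteria joined by *or*: the observed treatment difference, or the "percent slowing (treatment difference divided by the placebo change) is equal to or greater than the corresponding values". The benchmarks and the consequence follow: "corresponding values from the STEADFAST pooled analysis (-0.92; -61%), this will be considered proof of concept". The footnote adds no condition on the sign of the placebo change, the sign of the difference, or the size of the denominator.

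SAP Section 1.6 is the only other place where -0.92 appears. For the cognitive composite it says: "The estimates of standard deviation and effect size for the change from baseline were -0.92 and 1.5, respectively". It then gives 49% power and an expected p-value of 0.052 at N = 43. For ADAS-cog it says: "The estimates of standard deviation and effect size for the change from baseline in ADAS-Cog was 3.4 and -1.54 respectively".

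Neither document reports a pooled STEADFAST placebo change at Month 6. The nearest figure is in Protocol Section 1.1.3, which notes "differences in rate of placebo decline in ADAS-cog between the STEADFAST study (3 points in 18 months" in the overall study.

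**The concern.** There are two separate problems.

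**Direction.** Higher ADAS-cog scores are worse, so decline is a positive change and benefit is a negative difference. A ratio of difference to placebo change measures slowing only while placebo declines. If placebo improves, the denominator changes sign and the rule inverts: harm gives a negative ratio and benefit a positive one. Over six months in mild disease, with about 21 patients per arm, the placebo mean may well land near or below zero.

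**Benchmark.** A threshold defined as difference over placebo change should be traceable to a placebo change. The only figures in the SAP that yield -61% are an effect and an SD.

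Either criterion is enough on its own and no significance is required. SAP Section 1.6 puts power for ADAS-cog at 30%, so this fallback may well decide how Part 1 is read. Part 1 in turn informs the design of Part 2.

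**Working it through.** **1. Which of -0.92 and 1.5 is the SD (SAP 1.6)?** The sentence names the SD first, but an SD cannot be negative. Check by two-sample t-test, 21 v 22 patients, two-sided alpha 0.05:

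- Effect 0.92, SD 1.5: SE = 1.5 × √(1/21 + 1/22) = 0.458; t = 0.92/0.458 = 2.01. Power is 50% and p = 0.051, against 49% and 0.052 stated.
- Labels taken literally (effect 1.5, SD 0.92): power 99.9%.
- Same method for ADAS-cog (1.54, SD 3.4): 30.5% and p = 0.145, against 30% and 0.144 stated.
- Modified composite (1.73, SD 2.9): 48% and p = 0.057, against 47% and 0.059 stated.

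So 1.5 is the composite's SD, and the two labels are transposed.

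**2. What gives -61%?** Effect/SD for the three endpoints:

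- Composite: -0.92/1.5 = -61.3%
- ADAS-cog: -1.54/3.4 = -45.3%
- Modified composite: -1.73/2.9 = -59.7%

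Only the pair containing the footnote's own -0.92 matches. Under the footnote's definition, -61% needs a placebo change between 0.92/0.615 = 1.50 and 0.92/0.605 = 1.52. That value is not reported.

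**3. Direction.** Let P and A be the placebo and active mean changes, with the criterion (A - P)/P ≤ -0.61.

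- P > 0: equivalent to A - P ≤ -0.61P, a benefit, as intended.
- P = 0: undefined.
- P < 0: equivalent to A - P ≥ 0.61|P|, so active must be *worse* by at least 61% of the placebo improvement. P = -0.5, A = +0.5: difference +1.0, ratio -200%, passes. P = -1.0, A = -0.3: difference +0.7, ratio -70%, passes.
- Literal numerical reading (ratio ≥ -61%): a ratio of 0, meaning no effect, passes.

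**4. How often an inert drug passes (signed reading).** Simulated arm means are normal with SE = SD/√n and the same true change in both arms, 22 placebo and 21 active. Swapping the arm sizes moves results by about one percentage point at most. The placebo decline is an assumption, shown as a range. The value 1.0 is 3 points in 18 months scaled linearly to 6 months (3 × 6/18).

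| SD | Assumed placebo decline | Ratio met | Ratio met with active worse (of all trials) |
|---|---|---|---|
| 3.4 (ADAS-cog) | 0.5 | 50% | 20% |
| 3.4 | 1.0 | 29% | 8% |
| 3.4 | 1.5 | 14% | 2% |
| 3.4 | 3.0 | 1% | 0% |
| 1.5 (composite) | 0.5 | 25% | 6% |
| 1.5 | 1.0 | 4% | 0.1% |
| 1.5 | 1.5 | 0.5% | 0% |

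**5. What the ratio adds to the -0.92 criterion.** At SD 3.4 the SE of the difference is 3.4 × √(1/21 + 1/22) = 1.037. An inert drug reaches -0.92 with probability Φ(-0.92/1.037) = Φ(-0.887) = 19%. Either criterion is met in about 51%, 33%, 22% and 19% of trials at declines of 0.5, 1.0, 1.5 and 3.0. The ratio therefore adds about 32, 14, 3 and 0 percentage points. The two criteria coincide at a placebo decline of 0.92/0.61 = 1.51; below that the ratio is the easier one. At a decline of 1.0 it asks for only 0.61 points.

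**The case against.** **On the benchmark.** A reader might infer that -61% has been shown to be effect over SD instead of difference over placebo change. The documents do not support that. The match is to two digits, no derivation is given, and a pooled placebo change of about 1.5 would make the figure correct as defined. Such a value is not implausible if -0.92 is in ADAS-cog points: linear scaling gives about 1.0 at Month 6 for STEADFAST overall, and Protocol 1.1.3 says diabetic placebo patients declined numerically more. This part of the objection stands. What is shown is a coincidence and a missing denominator, not an arithmetic error.

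**On direction.** The word slowing presupposes decline, and the alternative hypothesis is worded as superiority, so a sensible analyst would not report a worse active arm as slowing. Figure 1 of the SAP, which illustrates the scheme, is not available here. That makes misuse less likely, but the footnote is the operative text and states no such condition. A placebo arm that merely fails to decline is not enough for a harmful pass: at zero change the ratio is undefined, so placebo must actually improve.

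**On size.** The 29% figure rests on the ADAS-cog SD and an all-comer decline. With the composite's SD, or with the faster decline suggested for diabetic patients, the rates are much lower. The -0.92 criterion is also lenient by itself. These points stand, which is why both SDs and the increments are shown above.

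**Conclusion.** The rule is deficient as written. The percent-slowing criterion can be met by a harmful result when the placebo arm improves, is undefined at zero placebo change, and on its literal wording admits no effect. This follows by algebra and needs no assumption.

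The frequency does depend on assumptions: arm means compared directly, no dropout, a placebo decline that the documents do not give at Month 6, and the choice of SD. On the ADAS-cog SD the ratio's own contribution to false proof of concept runs from about 32 percentage points at a decline of 0.5 to none at 3.0. On the composite SD the ratio is met in 25% of trials at 0.5 and hardly at all at 1.5.

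The -61% benchmark is probably a standardised effect, but this cannot be proved from the documents. The sponsor can settle it by stating one number.

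The formal test of ADAS-cog14 and the testing hierarchy are unaffected. What is at risk is the proof-of-concept claim from Part 1.

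**What to change.** In SAP Section 2, footnote *, before Part 1 is unblinded:

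- **Direction.** Count percent slowing only if the placebo arm worsened and the treatment difference favours azeliragon. State the criterion as a reduction in decline of at least the benchmark, so that the sign of the inequality is not in question. Otherwise report percent slowing as not evaluable. Cost: a sentence or two of text, and a criterion that is slightly harder to meet.
- **Benchmark.** Check -61% against the STEADFAST pooled Month 6 placebo change for the named scale, and print that denominator. If the figure proves to be effect/SD, either replace it with difference/placebo change, or relabel it as a standardised effect and compare it with the Part 1 difference/SD. Cost: one recalculation from existing STEADFAST output. The threshold may become harder or easier: with -0.92 as the difference, a placebo change of 1.0 would give -92%, 2.0 would give -46% and 3.0 would give -31%.
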